1.1.2.2 Nonclinical Pharmacokinetics and Metabolism

The pharmacokinetics (PK) of ATI-450 was studied in mouse, rat, dog, monkey, and mini-pigs. The single dose intravenous PK in all nonclinical species is characterized by a mono-exponential pattern of elimination with mean half-lives ranging from 0.5 to 3.1 hours. After oral dosing, the mean half-life ($t_{1/2}$) was observed to be up to 6.33 hours in the monkey. Clearance was low in dog and monkey; and high in rat and mouse. Oral bioavailability was high in mouse; moderate in rat, dog, and monkey; and lower in mini-pig.

ATI-450 has the potential to translate the observed pre-clinical efficacy into the clinic based upon its oral drug-like properties. Metabolic stability and PK properties of ATI-450 (e.g., long $t_{1/2}$, low clearance, high oral bioavailability, high volume of distribution) are consistent with oral, 1 to 2 times per day dosing in humans.

1.1.2.3 Toxicology and Safety Pharmacology

In vitro, no appreciable off-target interactions were observed in broad profile screening against receptors, enzymes, and transporters relevant for safety evaluation. No significant inhibition of the human ether-a-go-go-related gene potassium channel current was observed in vitro. In a standard battery of in vivo safety pharmacology studies, no AEs of ATI-450 were found on the respiratory and central nervous systems following single dose oral administration up to 45 mg/kg in rat. In a cardiovascular study in mini-pig, no ATI-450-related changes in ECG waveform (PR interval, QRS interval, and corrected QT interval [QTcB]) were observed; however, ATI-450 administration at a dose level of 45 mg/kg was associated with a decrease in arterial BP approximately 2 through 6 hours post-dose, and an elevated heart rate and body temperature approximately 7 through 18 hours post-dose. Arterial BP returned to baseline by 8 hours post-dose, with heart rate and body temperature returning to baseline by 24 hours post-dose. No effects were noted in animals given 5 or 15 mg/kg.

ATI-450 was not genotoxic in the bacterial reverse mutagenicity assay or in the in vitro chromosomal aberration assay using cultured human peripheral blood lymphocytes, or in an in vivo micronucleus assay in the rat.

Thirteen-week oral toxicity studies were conducted in rats and mini-pigs at dose levels of 3, 10, and 30 mg/kg/day and 10, 30, and 60 mg/kg/day, respectively. There were no ATI-450-related adverse effects noted in either species. ATI-450-related findings in rats given oral doses up to 30 mg/kg/day included a mild to moderate myocyte degeneration, which did not have any effect on the health and well-being of the animals and was not observed after a 4-week non-dosing recovery period. There were no adverse effects on clinical pathology (hematology, clinical chemistry, coagulation, urinalysis). In mini-pigs given oral doses up to 60 mg/kg/day, sporadic and transient clinical signs of warm to touch and hypoactivity were observed once or twice during the 13-week dosing period in 1 or 2 animals given 30 or 60 mg/kg/day. As these were isolated incidences, they were not considered to be adverse. No adverse effects of treatment were observed on clinical pathology (hematology, clinical chemistry, coagulation, urinalysis), nor were there any gross post-mortem or histopathologic findings observed in mini-pigs after 13 weeks of daily oral treatment.

Based on the results of the 13-week oral toxicity studies in rats and mini-pigs, the No-Observed-Adverse-Effect Level was considered to be 30 mg/kg/day in rats and 60 mg/kg/day in mini-pigs.

In conclusion, ATI-450 selectively blocks p38α activation of the proinflammatory kinase MK2 while sparing p38α activation of other effectors such as PRAK and ATF2. Through this mechanism, ATI-450 inhibits inflammatory pathways (such as TNF-α and IL-1β), implying it has potential in a broad range of inflammatory indications. By avoiding direct inhibition of p38, which could lead to inhibition of anti-inflammatory substrates of p38, ATI-450 has the potential to avoid transient efficacy associated with global p38 inhibitors.

1.1.3 Clinical Studies

A single and multiple dose ascending study of ATI-450 in healthy volunteers has been conducted: ATI-450-PKPD-101.

ATI-450-PKPD-101 consisted of multiple parts. A total of 32 male and female subjects were enrolled into Part A of the study where 4 ascending single doses (10 mg, 30 mg, 50 mg, and 100 mg) were explored. Eight subjects were randomized at each dose level to receive a single oral dose of ATI-450 (n=6) or placebo (n=2). The 50 mg cohort was repeated following a high fat, high calorie breakfast to explore the fed-fasting PK of ATI-450.

In Part B, 3 ascending multiple doses (10 mg BID, 30 mg BID, and 50 mg BID) were explored in 30 male and female subjects. Ten subjects were randomized to receive multiple oral doses (6.5 days) of ATI-450 (n=8) or placebo (n=2) at each dose level.

Data demonstrates that ATI-450 was well tolerated at all doses in the study. No SAEs or severe intensity events were reported. The most common AEs (reported by 2 or more subjects who received ATI-450) were dizziness, headache, upper respiratory tract infection, constipation, and abdominal pain. All events were of mild intensity. A trend of a decrease in ANC was observed concurrent with dosing of ATI-450 without correlated clinical sequelae. No subject had an ANC value <500 cells/ μ L. Other laboratory findings were generally unremarkable.

After single oral doses (10 mg to 100 mg), ATI-450 was rapidly absorbed with median time to maximum plasma concentration (t_{max}) values ranging from 2.0 to 4.0 hours. Systemic exposure to ATI-450 (as measured by mean maximum plasma concentration [C_{max}] and area under the concentration-time curve from time 0 to infinity [AUC_{0-∞}]) increased approximately proportionally with dose between 10 and 100 mg, suggesting that the PKs of ATI-450 are dose-independent (i.e., linear) over the dose range evaluated. Elimination of ATI-450 from plasma was moderately slow, with mean terminal half-life $t_{1/2}$ values ranging from approximately 9 to 11 hours. After oral administration of ATI-450 at 100 mg with a standardized high fat, high-calorie breakfast, the median t_{max} was delayed (6.0 hours versus 2.0 hours), but there did not appear to be any appreciable impact on systemic exposure to ATI 450 (C_{max} was ~14% lower and AUC_{0-∞} was ~10% higher in the fed state).

The PK behavior of ATI-450 after multiple dose administration was consistent with that observed following single doses. Trough concentrations of ATI-450 were generally similar on Days 2 through 7, suggesting that the subjects were at or near steady-state by Day 2 of BID administration. Systemic exposure to ATI-450 on Day 7 of dosing was approximately dose-proportional between 10 and 50 mg. A small amount of accumulation (up to 1.4-fold) was observed following multiple dosing, which was not unexpected given the $t_{1/2}$ of ATI-450 and the length of the dosing interval.

The PD of ATI-450 were explored by investigating the inhibition of cytokines of interest in blood samples collected from subjects in ATI-450-PKPD-101. For 10 mg BID, mean trough drug levels were below the 80% inhibitory concentration (IC80) for IL-1 β and TNF α . At 30 mg BID, mean trough drug levels were above the IC80 for IL-1 β , but not for TNF α . At 50 mg BID,

mean trough drug levels were above the IC80 for IL-1 β and TNF α . No dose level achieved mean trough levels above the IC80 for IL-6, but the 50 mg BID dose level produced drug levels that were higher than the IC50 for IL-6 for at least part of the dosing interval.

The safety, PK, and PD data support the 50 mg BID dose level as the most appropriate for investigation in this study.

1.2 Study Rationale

The assessment of 12-weeks of ATI-450 treatment in patients with CAPS will provide important data to initially explore the safety and efficacy of ATI-450 in patients with CAPS.

CAPS is a rare hereditary autoinflammatory disease caused by a gain-of-function mutation of the NLRP3 gene coding for cryopyrin, which is a component of the NLRP3 inflammasome. Dysregulation of the NLRP3 inflammasome results in an overproduction of IL-1, and consequently the inflammatory symptoms seen in CAPS¹. Current anti-IL-1 therapies have been shown to induce rapid and sustained disease remission in CAPS patients and are generally well tolerated ^{2, 3, 4}.

ATI-450 has been shown to cause a marked inhibition of IL-1 in both pre-clinical and clinical studies. Current anti-IL-1 therapies for treatment of CAPS are biologics that are administered either intravenously or subcutaneously. ATI-450, an orally administered small molecule, has the potential to have a similar safety and efficacy profile compared to currently available therapies with a differentiated route of administration that may be preferred by some CAPS patients.

This study is being conducted to determine the safety, tolerability, PD, and preliminary efficacy of ATI-450 in patients with CAPS. The results of this study may support further investigation of ATI-450 in patients with CAPS.

1.3 Benefit/Risk Assessment

Efficacy data for ATI-450 in the intended indication of CAPS are not yet available.

In non-clinical repeat-dose toxicology studies, incidence of skeletal muscle degeneration was noted in 3 muscles (psoas, quadriceps femoris, and soleus) in 1 species only, and was attributed to ATI-450 treatment. However, there was no evidence of persistence of these findings, suggesting that the lesions were fully reversible following discontinuation of dosing. The risk to humans associated with these toxicology findings are anticipated to be very low in this short clinical study. There are also theoretical risks similar to what has been observed for other anticytokine therapies, such as serious infections, malignancy, cytopenia(s), and hypersensitivity reactions. Data from the first-in-human study ATI-450-PKPD-101 demonstrate ATI-450 was generally well tolerated with no SAEs, severe adverse events, or AEs that led to discontinuation of study medication. The most common AEs (reported by 2 or more subjects who received ATI-450) observed during the trial were dizziness, headache, upper respiratory tract infection, constipation, nausea, and abdominal pain. All AEs were mild. A trend of a decrease in ANC was

Sponsor Name: Aclaris Therapeutics Inc. Protocol Number: ATI-450-CAPS-201 Version and Date: 2.0 24 Sep 2020

Page 25 of 71

observed without correlated clinical sequelae. This effect is consistent with the PD profile of certain anti-TNF therapies⁷. Other laboratory findings were generally unremarkable.

More detailed information about the known and expected benefits, risks, and reasonably expected AEs of ATI-450 can be found in the Investigator's Brochure (IB).

Sponsor Name: Aclaris Therapeutics Inc. Protocol Number: ATI-450-CAPS-201 Version and Date: 2.0 24 Sep 2020

2 STUDY OBJECTIVES AND ENDPOINTS

The objectives and endpoints for this study are provided in Table 2 below.

Table 2 Study Objectives and Endpoints

Objectives		Endpoints			
Primary	To assess the safety and tolerability of ATI-450 to maintain remission in patients with CAPS previously managed with anti-IL-1 therapy	Number and percent of adverse events (AEs) and serious adverse events (SAEs); mean change from baseline in laboratory values, vital signs, and electrocardiograms (ECGs).			
Secondary	To assess the efficacy of ATI-450 to maintain remission in patients previously managed with anti-IL-1 therapy	 Proportion of participants in disease remission. Disease remission is defined as having a Physician Global Assessment (PGA) score of absent or minimal and a high sensitivity C-reactive protein (hsCRP) and serum amyloid A (SAA) value within the normal range (≤10 mg/L) or within 30 percent of the baseline value. Proportion of participants in clinical remission. Clinical remission is defined as having a PGA score of absent or minimal. Time to relapse; where relapse is defined as a two-point worsening on the PGA scale. Proportion of participants who experience a re-emergence of disease symptoms after discontinuation of ATI-450. Re-emergence is defined as an increase in daily Key Symptom Score (KSS) ≥3 for at least two consecutive days. KSS is derived from the patient-administered daily health assessment form (DHAF). Proportion of participants with a mean KSS no more than 2 points higher than baseline for at least 6 out of 8 weeks during the treatment period. Change from baseline in PGA. Change from baseline in PGA. 			

		Change from baseline in hsCRP and SAA.
Exploratory	 To assess the Pharmacodynamics (PD) of ATI-450 in patients with CAPS To assess the pharmacokinetics (PK) of ATI-450 in patients with CAPS 	 Change from baseline in serum cytokines IL-1β, IL-1α, IL-6, IL-18 and TNF-α ATI-450 concentrations at trough

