4.4 Premature Discontinuation

4.4.1 Premature Discontinuation of Investigational Product

Patients should discontinue ATI-450 if any of the following occurs:

- Serious infection
- Invasive fungal infection
- Malignancy (except for non-melanoma skin cancer)
- Hepatitis B virus reactivation

- Demyelinating disease
- Heart failure
- Lupus-like syndrome
- Hypersensitivity reaction
- Gastrointestinal perforation
- WBC count: $<1\times10^3/\mu$ L
- ANC: $<0.5 \times 10^3 / \mu L$
- Lymphocyte count: $<0.3\times10^3/\mu$ L
- Platelet count: $<50\times10^3/\mu$ L
- Hemoglobin: <6.5 g/dL
- AST or ALT:
 - o ≥5×ULN persisting for 2-weeks after study medication interruption or second occurrence of ≥5×ULN
 - \circ ≥3×ULN and total bilirubin ≥2×ULN or international normalized ratio [INR] >1.5
 - ≥3×ULN with appearance of fatigue, nausea, vomiting, right upper quadrant pain or tenderness, fever, rash, and/or eosinophilia (>5%)
- Serum creatinine: >2×ULN persisting for 2-weeks after study medication interruption or second occurrence of >2×ULN
- Confirmed, active infection with the severe acute respiratory syndrome coronavirus 2 (SARS-CoV-2 virus)
- The patient withdraws his/her consent to participate in the study
- The patient develops an illness that would interfere with his/her continued participation in the study
- The patient is noncompliant with study procedures or medication, in the opinion of the investigator
- The patient is confirmed to be pregnant
- The sponsor or regulatory agency requests withdrawal of the patient

- Severe AEs or SAEs
- Any other reason relating to the patient's safety

The investigator will make every effort to ensure that patients who prematurely discontinue ATI-450 complete the end of study assessments.

Patients who discontinue ATI-450 prematurely may be replaced at discretion of the sponsor.

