8.4.2 Safety Analyses

The Safety population will be used for the analysis of safety data (AEs, exposure to study medication, clinical laboratory, vital signs, and ECG).

AEs will be coded with the MedDRA. TEAEs are defined as AEs with an onset date on or after the date of first administration of study medication and before the date of last administration of study medication + 30 days. TEAEs will be presented by system organ class and preferred term in frequency tables. Patients with multiple AEs will be counted only once within each preferred term and system organ class. Key patient information for patients with an AE with an outcome of death, patients with SAEs, and patients with an AE leading to discontinuation of study medication will be listed.

Laboratory data (hematology, serum chemistry, coagulation, lipids, and urinalysis) will be converted to Système International units for reporting and processing purposes. Absolute values and changes from baseline will be presented descriptively. Laboratory data outside study-specific reference ranges will be listed.

Vital signs and ECG parameters will be presented descriptively.

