8.4.5 Handling of Missing Values

Missing data will not be imputed for the safety summaries or the efficacy summaries conducted on the PP population.

For efficacy summaries conducted on the ITT population a model based multiple imputation procedure will be used to impute missing data, where appropriate. Rules for imputation of missing efficacy data will be detailed in the SAP.

Patients who prematurely discontinue the study will be evaluated based on the data collected at each visit attended. Data collected during the withdrawal visit will be used as an end of study assessment for these patients. If the withdrawal visit was performed >1 day after the last dose was administered, then the previous visit will be used as the end of study assessment.

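### The previous-visit rule in 8.4.5 does not exempt safety data, so an early stopper's observed value can be lost from the primary mean changes; for ECG no on-treatment value can replace it

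*Combined protocol and SAP*

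**What the plan says.** Section 2, Table 2 gives the primary endpoint two parts: "Number and percent of adverse events (AEs) and serious adverse events (SAEs", and "mean change from baseline in laboratory values, vital signs, and electrocardiograms (ECGs". No time point is named for the mean changes. For laboratory data, Section 8.4.2 says "Absolute values and changes from baseline will be presented descriptively", and it treats vital signs and ECG parameters descriptively too.

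Section 8.4.5 handles incomplete data in three steps:
- "Missing data will not be imputed for the safety summaries or the efficacy summaries conducted on the PP population".
- "Patients who prematurely discontinue the study will be evaluated based on the data collected at each visit attended", with the withdrawal visit serving as their end-of-study assessment.
- If the withdrawal visit was more than 1 day after the last dose, "then the previous visit will be used as the end of study assessment".

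Section 4.4.1 lists laboratory thresholds at which ATI-450 is stopped (WBC, ANC, lymphocytes, platelets, haemoglobin, AST/ALT, creatinine). It asks the investigator to try to have those patients "complete the end of study assessments". Section 4.4.2 asks for the Day 84 and follow-up Day 7 assessments from patients who leave the study. Table 1 schedules laboratory tests and vital signs at every clinic visit, but ECG only at screening, Day 1 and Day 84.

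**The concern.** The previous-visit rule is not confined to efficacy endpoints. Applied to the primary safety means, it sets aside a measurement that was made and puts an earlier one in its place. The patients affected are those who stopped early, some of them because of the variables being averaged. Where the later value is the abnormal one, the mean moves toward no effect.

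Three gaps add to this:
- The rule speaks of discontinuing the study. Sections 4.4.1 and 4.4.2 separate stopping the drug from leaving the study, and Appendix 1 allows a patient to stop the drug and stay for follow-up. Section 8.4.5 does not say how that patient is handled.
- No section asks for the remaining scheduled treatment-period visits after the drug is stopped, so the patient is absent from the visit means in between.
- Section 5.3.2 requires clinically significant laboratory abnormalities to be repeated, but Section 8.4.2 does not say how unscheduled results enter a summary. A value seen only on a repeat enters no planned visit mean.

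With up to 10 patients, one such value can make up much of a mean. A fall in ANC has already been reported with ATI-450 (Sections 1.1.3 and 1.3).

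**Working it through.** The plan has no figure of its own to reproduce. The sample size in 8.3 rests on feasibility, and no SD, effect size or dropout rate is given. All changes and stopping rates below are assumptions; the structure comes from the sections named.

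**ECG.** Take n = 10, k early stoppers with change x, and the others with mean change m. If the withdrawal ECG is more than 1 day after the last dose, the text allows three readings:
- Withdrawal ECG used: (k·x + (n − k)·m)/n
- Withdrawal ECG dropped, no value: m
- Previous ECG carried. Visits 3 to 5 have none, so this is Day 1 and the change is 0: (n − k)·m/n

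For k = 1, x = +40 and m = +2 msec:
- used: (40 + 9 × 2)/10 = +5.8
- dropped: 18/9 = +2.0
- carried: 18/10 = +1.8

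Other assumed values:

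| k | x | m | used | dropped | carried |
|---|---|---|---|---|---|
| 1 | 30 | 5 | 7.5 | 5.0 | 4.5 |
| 1 | 60 | 5 | 10.5 | 5.0 | 4.5 |
| 2 | 60 | 5 | 16.0 | 5.0 | 4.0 |

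**Laboratory values.** Section 8.4.5 normally keeps a stopped patient in the end-of-study mean. Suppose nine patients' ANC falls by 0.5, and one falls from 3.0 to 0.4 (× 10³/µL, change −2.6) at the Day 28 visit and is stopped under the <0.5 threshold.
- Day 28: (−2.6 + 9 × −0.5)/10 = −0.71
- Day 56, patient absent: −0.50
- End of study, withdrawal visit more than 1 day after the last dose: the previous visit is Day 28, so the mean is again −0.71

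The gap here is at Day 56, not at the end of study. An end-of-study loss needs the abnormal value to appear first at a late withdrawal visit, or only on an unscheduled repeat that is not taken as the previous visit. The late visit is sometimes built in: one AST/ALT criterion and one creatinine criterion in 4.4.1 require persistence for 2 weeks after interruption. A patient who meets either is already well past 1 day off drug. The earlier elevated value survives only if the previous visit recorded it. Vital signs behave like laboratory values.

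**How often someone stops.** P(at least one of 10 stops) = 1 − (1 − p)¹⁰, which is 0.40, 0.65 and 0.89 for p = 5%, 10% and 20%. This covers stopping for any reason. The fallback also needs a late withdrawal visit, so these are upper limits on how often it applies.

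**The case against.** A reader might infer more: that a patient stopped for toxicity leaves every later mean, so that the Day 84 figures describe only patients who tolerated the drug. The documents do not support that. Section 8.4.5 places the withdrawal visit, or failing that the previous visit, in the end-of-study assessment, and 4.4.1 and 4.4.2 both ask for those assessments. In the ANC example the low value is retained. Nor does 4.4.1 take patients off drug for ECG values: it has no ECG or QTc threshold. The ECG point rests on Table 1 and 8.4.5 alone.

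The harm is also recorded elsewhere. AE and SAE counts are part of the same primary endpoint. Section 7.1.3 requires laboratory abnormalities that lead to discontinuation to be recorded as AEs or SAEs, and 5.3.4 and 5.3.5 do the same for clinically significant ECG and vital-sign findings. Section 8.4.2 lists out-of-range laboratory values and AEs leading to discontinuation. Section 8.1 reports n, minimum and maximum. All of this stands and rules out concealment. It does not correct the means, and a visit's minimum and maximum cover only the values admitted to that visit.

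Two further defences have weight. The statement that "Missing data will not be imputed for the safety summaries" could be read as barring the replacement. But the replacement chooses which observed visit counts as the end of study; it sits in a separate paragraph with no stated limit, so the text does not settle the matter. Second, a value taken days after the last dose may not reflect exposure: Section 1.1.3 gives a half-life of about 9 to 11 hours, so 24 hours is 2.2 to 2.7 half-lives. That is a reason to label the value with time off drug, not to discard it from a safety summary.

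Finally, 8.1 leaves detailed methods to the SAP, so the absence of worst-value tables here does not prove that none will be made. It does mean the fix can still be placed there.

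**Conclusion.** The point holds in this limited form. Section 8.4.5 leaves open whether its previous-visit replacement applies to the primary safety means. If it does, an observed withdrawal value can be lost from them. For ECG there is no on-treatment fallback, and the same data give +5.8, +2.0 or +1.8 msec depending on the reading. For laboratory values the certain loss is at the scheduled visits between stopping and the end of study; an end-of-study loss arises only when the previous visit did not capture the abnormality. The sizes rest on assumed changes, one early stopper among ten, and a withdrawal visit more than 1 day after the last dose. The direction is toward no effect only where the discarded value is the more abnormal one. Because individual cases are visible elsewhere, this is a moderate fault in the continuous summaries, worth correcting before database lock.

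**What to change.** In 8.4.5:
- State that the previous-visit replacement does not apply to safety data.
- State that observed withdrawal laboratory, vital-sign and ECG values are summarised with days since last dose, both for patients who stop ATI-450 only and for those who leave the study.

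In 8.4.2:
- Keep the by-visit means.
- Add, for all treated patients, the worst post-baseline value and change per patient, drawn from scheduled, unscheduled and withdrawal measurements.
- Add the number of patients crossing each existing 4.4.1 laboratory threshold at any time.
- Name the population. This section refers to a Safety population that 8.2 does not define, while the synopsis uses ITT for safety.

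The cost is a few sentences and one or two tables from data already collected. No clinical rule changes. The drawback is that a per-patient extreme is sensitive to a single spurious reading, so it should stand beside the visit means and not replace them.
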